Large vessel occlusion (LVO) stroke causes around 30% of acute ischemic strokes (AIS) and is associated with severe deficits and poor neurological outcomes.¹⁻⁴ Endovascular thrombectomy (EVT) enormously improves the prognosis of patients with LVO stroke, but its effect is highly time-dependent. Because of its complexity and required resources, EVT can be performed in selected hospitals only. In the Netherlands, approximately half of the EVT-eligible patients are initially admitted to a hospital incapable of performing EVT, and – once it has been ascertained that a patient requires EVT – the patient needs to be transported a second time by ambulance to an EVT-capable hospital.⁵ This workflow leads to an average treatment delay of about 1 hour, which decreases the absolute chance of a good outcome of the patient by 5-15%.⁵⁻ ⁷ To solve this issue, a prehospital stroke triage instrument is needed, which reliably identifies LVO stroke in the ambulance, so that these patients can be brought directly to an EVT-capable hospital. Electroencephalography (EEG) may be suitable for this purpose, since it shows almost instantaneous changes in response to cerebral blood flow reduction.^{8,9} Moreover, significant differences between EEGs of patients with an LVO and those of suspected AIS patients with a smaller or no vessel occlusion have been found.¹⁰ A dry electrode EEG cap enables ambulance paramedics to perform an EEG in the prehospital setting, with significant reduced preparation time compared to conventional wet electrode EEG.^{11, 12} An automatic LVO-detection algorithm will be the key to reliable, simple and fast interpretation of the EEG by paramedics, enabling direct admission of suspected AIS patients to the right hospital.

HYPOTHESIS

An EEG-based algorithm, developed with artificial intelligence (AI), will have sufficiently high diagnostic accuracy to be used by ambulance paramedics for prehospital LVO detection.

OBJECTIVE

The primary objective of this study is to develop one or more novel AI-based algorithms (the AI-STROKE algorithms) with optimal diagnostic accuracy for identification of LVO stroke in patients with a suspected AIS in the prehospital setting, based on ambulant EEG data.

STUDY DESIGN

AI-STROKE is an investigator-initiated, multicenter, diagnostic test accuracy study.

STUDY POPULATION

Part A: Adult patients with a (suspected) AIS, in the prehospital setting.

Part B: Adult patients with a (suspected) AIS, in the in-hospital setting.

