4.4 SAMPLE SIZE CALCULATION

We aim to develop and validate a novel algorithm for diagnosis of LVO stroke. In the prehospital and inhospital setting together, EEG-measurements will be performed in a maximum of 1192 patients.

Using preliminary data of the ongoing ELECTRA-STROKE study (clinicaltrials.gov, NCT03699397), we identified two independent EEG predictors for LVO stroke: the theta-alpha ratio and the weighted phase lag index. For optimal algorithm development, using conventional statistical methods, 20-50 events (i.e. LVO strokes) per predictor are required in the derivation cohort.³⁰ Thus, with conventional statistics, 40-100 patients with an LVO stroke would be required for algorithm development. Based on an incidence of 12% for LVO stroke among patients with a suspected AIS³¹, and assuming a dropout rate of 30% (either due to missing consent or failed EEG registration), 484-1192 patients with a suspected AIS are required.

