8.5 REPLACEMENT OF INDIVIDUAL SUBJECTS AFTER WITHDRAWAL

Since our sample size calculation includes an expected dropout rate, we do not intend to replace subjects that have withdrawn from the study. However, if the drop-out rate is higher than anticipated or when the number of LVO stroke patients is lower than expected, the steering committee (as specified in Appendix

7) may decide on replacement at a later stage. Records will be kept of all reasons for withdrawal and these will be reported along with the study results.

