EEG data quality will be monitored continuously to avoid an excessive drop-out rate due to malfunctioning EEG hardware. Two interim analyses for the AI algorithms will be performed: the first when 50 and the second when 100 LVO stroke patients are included in the study. Results of these analyses will be obtained by performing k-fold cross-validation on the training data, including data from the ER and the ambulance. The diagnoses (i.e. LVO stroke or no LVO stroke) as predicted by the developed algorithms will be compared to the diagnoses given by the adjudication committee. A receiver operating characteristic (ROC) curve will be plotted for each algorithm and the optimal cut-off value (i.e. highest sensitivity at a specificity \geq 80%) for each algorithm will be determined. For these cut off values, the sensitivity, specificity, negative predictive value and positive predictive value will be reported, including 95% confidence intervals. The steering committee may decide to prematurely stop the recruitment in the study if the results of the interim analysis show that an accurate and stable algorithm can be developed with the data collected up till that point.

Eventually, we will evaluate the performance of the developed classification algorithm(s) and several existing algorithms on the validation data set. A receiver operating characteristic (ROC) curve will be plotted for each algorithm and the optimal cut-off value (i.e. highest sensitivity at a specificity \geq 80%) for each algorithm will be determined. For these cut off values, the sensitivity, specificity, NPV and PPV value will be calculated.

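### Accuracy is planned on the EEG recordings obtained, so it is conditional on a usable recording, while the stated question covers all suspected-AIS patients in the prehospital setting

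*Combined protocol and SAP*

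**What the plan says.** Section 4.4 inflates the sample size "assuming a dropout rate of 30% (either due to missing consent or failed EEG registration". The two causes share one figure and are not separated anywhere else. Section 8.5 relies on the same allowance: "Since our sample size calculation includes an expected dropout rate, we do not intend to replace subjects that have withdrawn from the study". It does let the steering committee revisit this, and it promises to report reasons for withdrawal.

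Section 10 uses the same vocabulary for hardware problems: "EEG data quality will be monitored continuously to avoid an excessive drop-out rate due to malfunctioning EEG hardware". It divides the EEG data obtained in the ambulance and the ER into 80% training and 20% validation. AUC (with success set at more than 0.80), sensitivity, specificity, PPV and NPV are all calculated on that validation set.

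The hypothesis in the Summary is that the algorithm "will have sufficiently high diagnostic accuracy to be used by ambulance paramedics for prehospital LVO detection". The first two secondary end points in section 8.1.2 are accuracy measures in suspected-AIS patients in the prehospital setting. Technical and logistical feasibility is a separate secondary end point, illustrated by channel reliability and limited to paramedics in the prehospital setting. No section defines a failed recording, assigns it a test result, or describes an analysis of all attempted recordings.

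**The concern.** For a triage test, a recording that cannot be read is one of the things that can happen when the test is used. The patient has a diagnosis: section 8.1.1 has the committee adjudicate all patients. What is missing is the algorithm's output. If such patients are left out, sensitivity and specificity describe the algorithm once a usable signal exists. That is a legitimate quantity, but it is not how often the test identifies LVO among the suspected-AIS patients to whom the cap is applied, which is what the hypothesis and the secondary end points address.

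Failure is not a remote possibility here. Section 3 says the hardware is being optimised after pilot findings, and section 2 makes cap reliability a secondary objective. A study could meet the AUC rule, report a separate failure rate, and still give no figure that combines the two. Without failure rates by LVO status, a reader could not reconstruct that figure.

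**Working it through.** **1. Do failed EEGs leave the sample in the plan's own arithmetic?** The inputs are all from section 4.4: "20-50 events (i.e. LVO strokes) per predictor are required in the derivation cohort" with two predictors, hence "40-100 patients with an LVO stroke would be required for algorithm development"; an LVO incidence of 12% in suspected AIS; and 30% dropout.

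Formula: N = events / incidence / (1 − dropout).

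- 100 events: 100/0.12 = 833.3, rounded up to 834; 834/0.70 = 1191.4, rounded up to 1192. This is the stated maximum: "EEG-measurements will be performed in a maximum of 1192 patients".
- 40 events: 40/0.12 = 333.3, rounded up to 334; 334/0.70 = 477.1, rounded up to 478. The plan states 484, a small difference that does not affect this point.

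In reverse, 1192 × 0.70 × 0.12 = 100 LVO patients. The target of 100 is therefore reached only after missing consents and failed EEGs have both been removed. The allowance covers 1192 × 0.30 = 358 patients, of whom 358 × 0.12 = 43 would have LVO at the plan's incidence. Only the failed-EEG part of these bears on this point, and the documents do not give that part.

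**2. Range for the failure share.** Let f be the share of failed EEGs among patients who do not drop out for missing consent, and c the share lost to consent. Then (1 − c)(1 − f) = 0.70. So f = 0 goes with c = 30%, f = 10% with c = 22.2%, f = 20% with c = 12.5%, and f = 30% with c = 0. All values of f below are assumptions within this range.

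**3. Sensitivity and specificity.** Assumed in usable recordings: Se = 0.70, and Sp = 0.80 (the floor in the cut-off rule of section 10). Failure is taken as equal in LVO and non-LVO patients.

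- Failures counted negative: Se(1 − f) and Sp(1 − f) + f.
- Failures counted positive: Se(1 − f) + f and Sp(1 − f).

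| f | Se, failed = negative | Sp, failed = negative | Se, failed = positive | Sp, failed = positive |
|---|---|---|---|---|
| 0% | 0.70 | 0.80 | 0.70 | 0.80 |
| 10% | 0.63 | 0.82 | 0.73 | 0.72 |
| 20% | 0.56 | 0.84 | 0.76 | 0.64 |
| 30% | 0.49 | 0.86 | 0.79 | 0.56 |

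Under either convention Se + Sp − 1 shrinks by the factor (1 − f): from 0.50 to 0.45 at 10% and 0.40 at 20%. With failures counted negative, the sensitivity result needs only the failure share among LVO patients. It does not need failure to be equal in the two groups.

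**4. AUC.** Failures are ranked lowest, with f1 the failure share in LVO and f0 in non-LVO patients:

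AUC = (1 − f1)(1 − f0)A + (1 − f1)f0 + 0.5·f1·f0.

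With f1 = f0 = f this reduces to 0.5 + (1 − f)²(A − 0.5). For A = 0.80:

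- f = 10%: 0.5 + 0.81 × 0.30 = 0.743
- f = 20%: 0.5 + 0.64 × 0.30 = 0.692

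With unequal failure:

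- f1 = 30%, f0 = 10%: 0.504 + 0.070 + 0.015 = 0.589
- f1 = 10%, f0 = 30%: 0.504 + 0.270 + 0.015 = 0.789
- f1 = 5%, f0 = 30%: 0.532 + 0.285 + 0.0075 = 0.82, above the usable-only value

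**The case against.** The clause in section 4.4 is a recruitment allowance for a derivation cohort. A model cannot be trained on an absent signal, so inflating for failed EEGs is right for that purpose and does not by itself define the validation set. Section 10 speaks of data obtained and sets no quality exclusion. A reader might infer that the plan expressly discards failed recordings; it does not say so. This stands: the exclusion is implied by the dropout arithmetic and the wording of section 10. But a failed registration yields nothing to score, and no other treatment is described, so following the text leads to the conditional estimate.

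A reader might also infer that the AUC in the success rule must be biased upward. That does not follow, because the last case in the working exceeds 0.80. Nor do the documents say which patients are harder to record. Hair quantity and length are recorded (section 8.3) without being linked to failure, and reduced consciousness is discussed only in relation to consent.

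Counting a failure as negative is a scoring convention. The documents do not say how a patient with a failed EEG would be handled in practice, and nothing here proposes a rule for that. This is why both conventions are shown.

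Finally, the primary objective is algorithm development, and reporting recordability apart from classification is defensible at that stage. That supports keeping the usable-only figures. It does not supply the missing ones: the feasibility end point omits the ER, although ER data are pooled into validation, and it has no breakdown by LVO status.

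**Conclusion.** The point holds in a limited form. The plan implies accuracy conditional on a usable recording, while its hypothesis and accuracy end points concern suspected-AIS patients in the prehospital setting.

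If a failed EEG gives no LVO signal, usable-only sensitivity overstates sensitivity among all attempted recordings whenever any LVO patient has a failed EEG. The size depends on an assumed failure share and an assumed usable-only sensitivity of 0.70. Specificity moves the other way under that convention. For AUC, a fall is established only when failure is unrelated to LVO status; otherwise the direction is open. If the whole 30% is missing consent, there is no effect.

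The sponsor should settle this before the validation set is analysed. It does not undermine the development of the algorithm.

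**What to change.** - **Section 10, definition.** Define a failed recording in terms that can be applied without knowing the diagnosis.
- **Section 10, split.** Allocate patients to training or validation before any quality filtering, so that failures belong to a set.
- **Section 10, analysis.** Beside the usable-only results in the validation set, add sensitivity, specificity, PPV and NPV for all patients with an attempted EEG whose data may be used. That means consent given, or death before consent was asked, as section 11.2 provides. Use the same cut-off as for the usable-only figures; the plan has no separately locked one. Count failures as algorithm-negative and, as a bound, as algorithm-positive.
- **Sections 4.4 and 10, reporting.** Report failed recordings separately from missing consent, by LVO status and by setting (ambulance or ER).
- **Interpretation.** State that usable-only accuracy and the AUC criterion are conditional on a usable recording.

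The cost is one extra table and, under the negative convention, a less favourable sensitivity. Sample size does not change. Two practical points need confirming: that consent is pursued whether or not the recording succeeded, which no section states, and that failures in the ER are logged as they are in the ambulance. Section 5 already plans technical information on the EEG in both parts once consent is given.

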5. TREATMENT OF SUBJECTS

PART A AND B

A single dry electrode cap EEG will be performed in the prehospital setting (part A) or at presentation in the ER (part B). As soon as feasible, preferably within 72 hours after arrival at the hospital or at discharge (whichever comes first), deferred informed consent is asked (see chapter 11). If informed consent is obtained, information on patient characteristics, medical history, medication use, physical and neurological examination performed by the treating physician, imaging studies, diagnosis and treatment as well as logistical and technical information regarding the patient's transport, treatment and the EEG measurement, obtained from the patient, the treating physician and the EMS will be collected. There are no follow up visits.

6. INVESTIGATIONAL PRODUCT

Not applicable, since no investigational product(s) will be used in this study.

7.NON-INVESTIGATIONAL PRODUCT

7.1 NAME AND DESCRIPTION OF NON-INVESTIGATIONAL PRODUCT

We will use the Waveguard[™] touch dry electrode EEG cap and compatible eego[™] mini amplifier (ANT Neuro B.V., Hengelo, Netherlands) to record and amplify the EEG signal, respectively. Both products are CE marked as medical devices in the European Union (Appendices 1 and 2) and will be used within the intended use as described in the user manuals (Appendices 4 and 5). To acquire the EEG signals from the amplifier, we plan to use CE marked NeuroCenter[®] EEG software (CE class IIa; Appendix 3 and 6) from Clinical Science Systems (ISO 9001 and ISO 13485 certified).

7.2 SUMMARY OF FINDINGS FROM NON-CLINICAL STUDIES

This is not relevant, as the Waveguard[™] dry electrode cap and eego[™] amplifier are both CE marked products that have been safely used in clinical studies (see chapter 7.3). NeuroCenter[®] EEG software is a CE class IIa product.

7.3 SUMMARY OF FINDINGS FROM CLINICAL STUDIES

The Waveguard[™] dry electrode cap and eego[™] amplifiers have both been safely used in several clinical studies, with no reported adverse events.^{11, 12, 32, 33} Two small studies that compared the Waveguard[™] dry electrode cap with conventional wet electrode EEG reported similar (good) wearing comfort as well as similar signal quality based on power spectral density analysis, with significantly less preparation time for the dry electrode cap.^{11, 12}

7.4 SUMMARY OF KNOWN AND POTENTIAL RISKS AND BENEFITS

Since an EEG-measurement is a safe and non-invasive procedure that is regularly performed in standard medical practice, and we only use CE marked products, we expect no health risks and no to minimal discomfort (during the measurement).^{11, 12} The caps will be cleaned and disinfected as recommended in by the manufacturer.

8. METHODS

8.1 STUDY PARAMETERS/END POINTS

8.1.1 MAIN STUDY PARAMETER/END POINT

Based on the EEG data one or more novel AI-based EEG algorithms (the AI-STROKE algorithms) will be developed with optimal diagnostic accuracy for identification of LVO stroke in patients with a suspected AIS in the prehospital setting. For the purpose of the study, an LVO is defined as an occlusion of:

- Intracranial part of the internal carotid artery (ICA)
- First segment or proximal part of the second segment of the middle cerebral artery (M1 and proximal M2, respectively)
- First segment of the anterior cerebral artery (A1)

The final diagnosis of all patients will be established by an adjudication committee, which will consist of a vascular neurologist and neuroradiologist, and will be based on available clinical and imaging data.

8.1.2 SECONDARY STUDY PARAMETERS/END POINTS

Secondary end points of this study are:

- AUC, sensitivity, specificity, positive predictive value (PPV) and negative predictive value (NPV) of the AI-STROKE algorithms based on ambulant EEG for diagnosis of LVO of the anterior circulation in suspected AIS patients in the prehospital setting;
- AUC, sensitivity, specificity, PPV and NPV of existing EEG algorithms based on ambulant EEG for diagnosis of LVO of the anterior circulation in suspected AIS patients in the prehospital setting;
- AUC, sensitivity, specificity, PPV and NPV of existing and newly developed EEG algorithms based on ambulant EEG for detection of LVO stroke of the posterior circulation, intracerebral hemorrhage, transient ischemic attack, and stroke mimics;
- Technical and logistical feasibility (e.g. in terms of EEG channel reliability) of paramedics performing ambulant EEG in patients with a suspected AIS in the prehospital setting.

8.2 BLINDING

In this diagnostic accuracy study, the treating clinical team and the paramedics are not blinded for the EEG recording. However, they are not trained nor instructed to interpret the EEG results in this study.

8.3 STUDY PROCEDURES

All collected data and study procedures are listed in the following table. There are no follow up visits. Items that are not part of standard medical procedure/treatment are bold.

	PART A	PART B
Patient characteristics*	<24 hours after arrival in hospital or at	<24 hours after arrival in hospital or at
	discharge (whichever comes first)	discharge (whichever comes first)
Past medical history	<24 hours after arrival in hospital or at	<24 hours after arrival in hospital or at
	discharge (whichever comes first)	discharge (whichever comes first)
Medication use	<24 hours after arrival in hospital or at	<24 hours after arrival in hospital or at
	discharge (whichever comes first)	discharge (whichever comes first)
Physical and neurological	At arrival in ER	At arrival in ER
examination by treating		
physician		
National Institute of Health	At arrival in ER	At arrival in ER
Stroke Scale (NIHSS) score		
Brain imaging results, if	At arrival in ER (if necessary, as judged	At arrival in ER (if necessary, as judged
available	by treating physician)	by treating physician)
Dry electrode cap EEG	At arrival of the ambulance	At arrival in ER
Final diagnosis, as judged by	At discharge	At discharge
the adjudication committee		
(as specified in Appendix 7)		
Treatment with IVT and/or	At arrival in ER (if necessary, as judged	At arrival in ER (if necessary, as judged
EVT	by treating physician)	by treating physician)
Times regarding stroke	Collected during first 24 hours after	Collected during first 24 hours after
logistics**	symptom onset	symptom onset

*Age, sex, estimated quantity and length of hair on the head of the participant.

**Time of: last seen well or witnessed stroke onset, 112-call, ambulance arrival on site, ambulance departure to hospital, ambulance arrival at hospital, start neuro-imaging (if any), start IVT/EVT (if any), transfer times from other primary hospital (if applicable), putting on EEG cap, start EEG measurement, stop EEG measurement.

8.4 WITHDRAWAL OF INDIVIDUAL SUBJECTS

Subjects can deny or withdraw consent at any time for any reason if they wish to do so without any consequences. The investigator can decide to withdraw a subject from the study for urgent medical reasons.

8.5 REPLACEMENT OF INDIVIDUAL SUBJECTS AFTER WITHDRAWAL

Since our sample size calculation includes an expected dropout rate, we do not intend to replace subjects that have withdrawn from the study. However, if the drop-out rate is higher than anticipated or when the number of LVO stroke patients is lower than expected, the steering committee (as specified in Appendix

7) may decide on replacement at a later stage. Records will be kept of all reasons for withdrawal and these will be reported along with the study results.

9. SAFETY REPORTING

9.1 TEMPORARY HALT FOR REASONS OF SUBJECT SAFETY

In accordance with section 10, subsection 4 of the Medical Research Human Subjects Act (in Dutch: WMO), the sponsor will suspend the study if there is sufficient ground to suspect that continuation of the study may jeopardize the health or safety of the subjects. The sponsor will notify the accredited METC without undue delay of a temporary halt including the reason for such an action. The study will be suspended pending a further positive decision by the accredited METC. The investigator will ensure that all subjects are kept informed.

9.2 AES, SAES AND SUSARS

9.2.1 ADVERSE EVENTS (AES)

Adverse events are defined as any undesirable experience occurring to a subject during the study, whether or not considered related to the investigational product or the intervention. All adverse events reported spontaneously by the subject or observed by the investigator or his/her staff will be recorded.

9.2.2 SERIOUS ADVERSE EVENTS (SAES)

A serious adverse event is any untoward medical occurrence or effect that:

- Results in death;
- Is life threatening (at the time of the event);
- Requires hospitalisation or prolongation of existing inpatients' hospitalisation;
- Results in persistent or significant disability or incapacity;
- Any other important medical event that did not result in any of the outcomes listed above due to but could have been based upon appropriate judgement by the investigator.

The sponsor will report the SAEs through the web portal *ToetsingOnline* to the accredited METC that approved the protocol, within 7 days of first knowledge for SAEs that result in death or are life threatening followed by a period of maximum of 8 days to complete the initial preliminary report. All other SAEs will be reported within a period of maximum 15 days after the sponsor has first knowledge of the serious adverse events.

Stroke often results in complications such as infections, delirium, constipation, decubitus wounds, swallowing difficulties and falls, as well as in hospitalization and death. Because we expect no health risk related to participation in this study, these events will be reported to the accredited METC that approved the protocol in a yearly line listing until the last patient has completed the study.

Furthermore, the following situations will not be reported as (S)AEs:

- Elective hospitalization for pre-existing conditions that have not been exacerbated by study treatment as judged by the clinical investigator and where admission did not take longer than anticipated;
- Admission and treatment for the index stroke (i.e. the stroke which lead to inclusion of the patient);
- Admission for diagnosis or therapy of a condition that existed before inclusion to this study and has not increased in severity or frequency as judged by the clinical investigator;
- Anticipated day-to-day fluctuations of pre-existing disease(s) or condition(s) present at the start of the study that do not worsen.

